#### *8.1.3.3 Pharmacodynamic Population*

Randomized subjects who receive study medication and have sufficient plasma concentration for analysis of the PD endpoints will be included in the pharmacodynamic analysis. Subjects with protocol violations will be assessed on a subject-by-subject basis for inclusion in the PD population. PD analysis will be conducted using the PD population.

Any additional analysis populations will be detailed in the Statistical Analysis Plan (SAP).

#### *8.1.4 Interim Analyses*

No interim analyses are planned for this study.

## **8.2 STUDY ENDPOINTS**

### *8.2.1 Primary Endpoints*

Primary endpoints include:

1. Safety:
  - Incidence, severity and causality of adverse events (AE) and serious adverse events (SAE)
  - Physical examination changes from baseline (days 4, 22, 56, and 90)
  - Vital sign changes from baseline (resting heart rate, systolic/diastolic blood pressure, respiratory rate, and temperature) (days 1, 4, 7, 10, 13, 16, 19, 22, 56, and 90)
  - Hematology and chemistry parameter changes from baseline (days 4, 22, 56, and 90)
  - 12 lead ECG changes from baseline (days 1, 4, and 22)
2. Tolerability as assessed by incidence and severity of injection site adverse events.

### *8.2.2 Secondary Endpoints*

The secondary endpoints of this study are to evaluate:

1. Efficacy as assessed by:
  - NIH Stroke Scale (days 22 and 90)
  - Barthel Index (days 22 and 90)
  - Modified Rankin Scale (days 22 and 90)
2. Plasma concentration of DM199 (days 2, 22, and 90)

3. Pharmacodynamics as assessed by:
  - Plasma C-reactive protein (CRP) (days 2, 22, and 90)
  - Plasma MMP-9 (days 2, 22, and 90)
  - Plasma VEGF (days 2, 22, and 90)
  - Plasma DM199 ADA (days 2, 22, and 90)

### 8.2.3 *Exploratory Endpoints*

Exploratory endpoints include:

1. Urinary KLK1 concentration (days 4, 13, 22 and 90)
2. Pharmacodynamics as assessed by:
  - Plasma tPA (days 2, 22, and 90)
  - Plasma Nitric Oxide as NOx (days 2, 22, and 90)
  - Plasma Prostaglandins (E2) (days 2, 22, and 90)

## 8.3 STATISTICAL METHODS

Data will be handled and processed according to the sponsor's representative (Novotech (Australia) Pty Ltd) Standard Operating Procedures (SOPs), which are written based on the principles of GCP.

All data collected on the eCRFs and results of central laboratory analysis will be presented in the data listings. All summaries will present the data by treatment group and overall (total subjects), as applicable.

Statistical methods will be primarily descriptive in nature. Each treatment group will be summarized separately. No formal statistical comparisons of DM199 versus placebo will be made.

The following statistical approaches will be taken:

- Continuous variables: Descriptive statistics will include the number of non-missing values (N), mean, standard deviation (SD), median, minimum, maximum. Additionally, for plasma concentrations of DM199, the coefficient of variation (CV%), geometric mean and geometric coefficient of variation (geo CV%) values may also be presented.
- Categorical variables: Descriptive statistics will include frequency counts and percentages per category.
- Imputation: No missing data will be imputed generally. The handling and presentation of plasma concentrations of DM199 below the limit of quantification (BLQ) will be discussed in the Statistical Analysis Plan.

- Confidence intervals (CIs): CIs will be two-sided and will use 95% confidence levels unless specified otherwise.
- Baseline: Baseline values will be defined as the last non-missing observation for each subject prior to the first dosing of study medication (i.e. start of infusion on Day 1).

Detailed statistical methods will be provided in a separate Statistical Analysis Plan (SAP) prior to data base lock.

### **8.3.1 Baseline Summaries**

Demographic and baseline characteristics will be summarized descriptively by treatment group.

### **8.3.2 Safety**

Safety endpoints will be analyzed using the Safety population.

#### **8.3.2.1 Adverse Events/Serious Adverse Events**

Adverse events (AEs) will be coded using the Medical Dictionary for Regulatory Activities (MedDRA®) and data will be summarized by System Organ Class (SOC) and Preferred Term (PT). The number and percent of subjects reporting each AE will be summarized for each treatment group and overall. A subject with two or more AEs within the same level of summarization (i.e., SOC or PT) will be counted only once in that level using the most severe (i.e., highest severity/grade) event or most related (for the relationship to study treatment table). Percentages will be based on the number of subjects in the Safety Population within each treatment group. The number of AEs reported will also be presented.

Treatment-emergent AEs (TEAEs) are defined as pre-treatment existing conditions that worsen after study treatment administration, or events that occur during the course of the study during or after administration of study treatment. Only TEAEs will be included in the AE summary tables which will present data by treatment group. In the case of a missing AE start date or stop date, the most conservative approach will be followed.

An overall summary of AEs will be produced including the number of TEAEs; the number and % of subjects reporting at least one: TEAE, serious TEAE, grade 3 or higher TEAE, TEAE related to study treatment (possible, probable), serious TEAE related to study treatment, grade 3 or higher TEAE related to the study treatment, TEAEs by maximum severity and TEAEs by maximum relationship, as appropriate.

Additional AE tables will be generated as follows, as appropriate:

- Overall TEAEs by SOC and PT
- TEAEs by Maximum Severity
- TEAEs by Maximum Relationship to Study Treatment
- Treatment Emergent SAEs

- TEAEs with Grade 3 or Higher
- Study Treatment Related TEAEs by SOC and PT
- Study Treatment Related TEAEs by Maximum Severity

A by-subject AE data listing, including verbatim term, MedDRA SOC and PT, severity, outcome and relationship to study treatment, will be provided. A separate listing will be generated for SAEs.

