**PROTOCOL SYNOPSIS**

PROTOCOL NUMBER	DM199-2017-001
PROTOCOL TITLE	A Randomized, Double-blind, Placebo-controlled Phase II Multi-Center Investigation to Assess the Safety and Tolerability of DM199 Administered Intravenously and Subcutaneously in Subjects with Acute Ischemic Stroke
STUDY PHASE	II
INVESTIGATIONAL PRODUCT (IP)	DM199
SPONSOR	DiaMedica Australia Pty Ltd [name] [name], Australia
NATIONAL PRINCIPAL INVESTIGATOR	[name] Royal Melbourne Hospital [name] [name], Australia
RESPONSIBLE CRO	Novotech [name] [name], Australia
CENTRAL LABORATORY	Sonic Clinical Trials [name] [name], Australia
STUDY RATIONALE	
DM199 is a recombinant human version of the KLK1 protein. In China, a urinary-derived form of this protein (Kailikang®) is approved as a treatment for acute ischemic stroke based on at least one large randomized, double-blind, placebo-controlled trial. The primary mechanism of KLK1 treatment appears to be an improvement of blood flow in capillaries and formation of new capillaries over the longer term. DM199 has been shown to be safe and well-tolerated in multiple Phase I and Phase IIA clinical trials. Moreover, these trials have demonstrated that DM199 can be dosed to achieve plasma exposures similar to those of Kailikang®.
 
DiaMedica Therapeutics Inc. is conducting this Phase II study in patients with acute ischemic stroke to establish safety and tolerability in this patient population. This study will also explore the effect of treatment on standard efficacy endpoints and biomarkers measured at various time points after the stroke. IV and subcutaneous routes of administration will be tested.

STUDY DESIGN	This is a randomized, double-blind, placebo-controlled Phase II, multi-center study of DM199. Subjects presenting with acute ischemic stroke will be randomized 1:1 to placebo or DM199

	administered by a single intravenous (IV) dose followed by subsequent subcutaneous (SC) doses.
OBJECTIVE	The objective of this study is to evaluate the safety and tolerability of DM199 in treating subjects presenting with acute ischemic stroke.

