### 2.4 STUDY DURATION

The duration of each subject's individual participation in the study will be 90 days from the time of consent to completion of all study activities. Subjects will receive 22 days of active treatment and will be followed for an additional 68 days.

It is estimated that approximately twelve months will be needed to recruit the total number of study subjects.

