### 5.11 SUBCUTANEOUS TREATMENT ADMINISTRATION

A single subcutaneous dose of DM199 or placebo will be administered between 2 and 12 hours after the start time of the IV dose. Additional doses will then occur every 72 ( $\pm$  2) hours after the first SC dose for the duration of the 22-day treatment period. In total, eight SC doses must be administered. Refer to **4. Study Treatment** and the pharmacy manual for information on proper storage, dosing, and administration.

Note: The treatment period (days 1-22) are defined by the time of the IV dose of study treatment rather than calendar days. Therefore, the first SC dose administered between 2 and 12 hours post IV may occur within the same calendar day or the day after. Caution should be taken to adjust all subsequent SC doses based on the required 72 ( $\pm$  2) window and required testing that is to occur on dosing days, including: body weight, height, and BMI calculation; vital sign measurements; urine sample for KLK1 concentration, and clinical labs.

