## 6.3 ADVERSE EVENT REPORTING

### 6.3.1 Reporting Period

Subjects will be evaluated for safety if they have received any treatment. Any preexisting conditions or signs and/or symptoms present in a subject prior to the start of the study (i.e., before informed consent) should be recorded as medical/surgical history. All AEs occurring after informed consent and on or before the final visit must be reported as AEs; only AEs that occur post-dose will be considered treatment-emergent. All AEs must be recorded irrespective of whether they are considered drug related.

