### 6.3.2 Adverse Event Collection

All AEs reported by the subject or noted in the medical record during the course of the study will be evaluated. At each encounter, subjects will be asked non-leading questions to determine the occurrence of AEs. AEs will be elicited using a standard non-leading question such as “How did you feel since last visit?” In addition, any signs or symptoms will be observed.

Adverse events may be collected from:

- The subject’s positive response to questions about their health
- Symptoms spontaneously reported by the subject
- Clinically relevant changes and abnormalities observed by the Investigator (e.g. local and systemic tolerability, laboratory measurements, results of physical examinations)

When an AE occurs, it is the responsibility of the Investigator to review all documentation relative to the event, including, but not limited to progress notes, laboratory, and diagnostic reports. The Investigator will then ensure that all relevant information regarding an AE is expediently recorded in accordance with the eCRF guidelines, including proper coding of the event term per the Medical Dictionary for Regulatory Activities (MedDRA). Investigators should be mindful of expedited reporting requirements for SAEs (refer to 6.5 Expedited Reporting of Serious Adverse Events). The Investigator will attempt to establish a diagnosis of the event based on signs, symptoms, and/or other clinical information. In all cases, when available, the diagnosis should be reported as the AE and not the individual signs/symptoms. It is not acceptable for the Investigator to send photocopies of the subject’s medical records to the Sponsor in lieu of completion of the appropriate AE eCRF pages.

The Investigator or designee will record all AEs in the source document as well as in each subject’s eCRF with information about:

- Adverse event and relevant clinical findings
- Time/date of onset
- Time/date of recovery or current status of adverse event

- Intensity/severity
- Action taken on study treatment
- Other action taken to treat the event
- Relation to study treatment
- Seriousness of the AE

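### Every planned AE table pools first dose to Day 90, so for events also common in stroke recovery an on-treatment excess is harder to see; tables by onset period should be added

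*Combined protocol and SAP*

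**What the plan says.** Three places define a treatment-emergent AE, and none closes the window. Section 6.2.1 takes any onset after study treatment, or worsening of a pre-existing condition. Section 6.3.1 says "only AEs that occur post-dose will be considered treatment-emergent". Section 8.3.2.1 takes worsened conditions and "events that occur during the course of the study during or after administration of study treatment". Collection runs to the last visit: "All AEs occurring after informed consent and on or before the final visit must be reported as AEs".

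On timing, Section 2.4 states: "Subjects will receive 22 days of active treatment and will be followed for an additional 68 days".

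On output, Section 8.3.2.1 states: "Only TEAEs will be included in the AE summary tables which will present data by treatment group". The listed tables are broken down by SOC and PT, severity, relationship, seriousness and grade. None is broken down by onset period. A subject is counted once per SOC or PT, at the worst grade or strongest relationship. Section 6.3.2 requires "Time/date of onset" to be recorded for each AE.

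On routes, the synopsis rationale says "IV and subcutaneous routes of administration will be tested". All subjects receive one infusion, and the first SC dose "will be administered between 2 and 12 hours after the start time of the IV dose" (Section 5.11).

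**The concern.** AE incidence is the first primary endpoint, and Section 8.3 rules out formal comparison of the arms. Safety will therefore be judged by setting percentages side by side, with about 33 subjects per group. In this population, complications of the stroke itself can be expected in both arms during follow-up. Where they share a term with a drug effect, both percentages rise and the contrast weakens.

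There is also a question of infusion tolerability. Severe infusion-related reactions are a listed reason for permanent discontinuation (Section 4.5), yet no AE table describes the hours between the infusion and the first SC dose.

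**Working it through.** **The plan's own timeline.** 22 + 68 = 90 days. Eight SC doses at 72-hour intervals fall on Days 1, 4, 7, 10, 13, 16, 19 and 22, as in Table 1. Share of the window after the last scheduled dose: 68/90 = 75.6%. This is not quite the same as time off drug, because Section 1.3 reports substantially longer exposure after SC than after IV dosing.

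**Assumptions.** The documents give no AE rates, so these are illustrative:
- background risk over 90 days p = 20%, constant hazard h = −ln(1 − p)/90 = 0.2231/90 = 0.00248 per day;
- drug effect lasting to Day 25 (Day 22 plus one 72-hour interval), hazard multiplied by R during that time;
- 33 subjects per arm (Section 8.1.2), no dropout.

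**Formulas.**
- 90-day risk on DM199: 1 − exp(−h(25R + 65)); on placebo: p.
- 25-day risk on DM199: 1 − exp(−25hR); on placebo: 1 − exp(−25h).

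**Main case, R = 2.**
- 90 days: 1 − exp(−0.00248 × 115) = 24.8% v 20.0%; difference 4.81 points, ratio 1.24.
- On treatment: 1 − exp(−0.1240) = 11.66% v 1 − exp(−0.0620) = 6.01%; difference 5.65 points, ratio 1.94.
- Excess subjects in 33: 33 × 0.0481 = 1.6 v 33 × 0.0565 = 1.9.
- Difference over its standard error, SE = √[(p₁(1 − p₁) + p₀(1 − p₀))/33]: 4.81/10.25 = 0.47 over 90 days, 5.65/6.95 = 0.81 on treatment.

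**Other assumed rates.**
- p = 40%, R = 2: ratio 1.20 over 90 days v 1.87 on treatment.
- p = 20%, R = 3: ratio 1.47 v 2.82.

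**If background events come early.** Keep p = 20% and R = 2, and place a share of the cumulative background hazard in the first 25 days.
- Share 50%: 28.4% v 20.0% (ratio 1.42) over 90 days; 20.0% v 10.6% (1.89) on treatment.
- Share 70%: 31.6% v 20.0% (1.58); 26.8% v 14.5% (1.86).

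The dilution shrinks but keeps its direction.

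**General form.** If a background risk q after treatment is common to both arms and independent of earlier events, the 90-day difference equals the on-treatment difference × (1 − q). In the main case q = 1 − exp(−65h) = 14.9%, and 5.65 × 0.851 = 4.81. For 10% v 30% on treatment (ratio 3.00), the 90-day ratio is 1.95 at q = 10%, 1.46 at 25%, 1.18 at 50%, and unchanged at q = 0.

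**The IV-only period.** It lasts 2 to 12 of 90 × 24 = 2,160 hours, or 0.09% to 0.56% of the window. Section 5.6 takes vital signs 30 minutes after the IV dose. Even if counted from the end of the 40-minute infusion, that is 70 minutes from its start, before the earliest SC dose at 2 hours. Section 5.9.1 takes Day 1 laboratory samples after IV and before SC. Sections 8.3.2.3 and 8.3.2.4 summarise vital signs, hematology and chemistry at all time points assessed. The gap in this period is therefore in the AE tables only.

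**The case against.** The strongest reply is that an open window is a defensible, conservative choice. The rationale points to new capillary formation over the longer term, and ADA and laboratory tests run to Day 90, so late effects matter. This stands, and it is why the 90-day tables should stay and should not give way to an on-treatment table as the basis of the safety conclusion.

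Second, ratios flatter the point. On the difference scale the main case loses under one point, or about 0.3 of a subject in 33. That is correct. What is lost is mainly precision: the difference falls from 0.81 to 0.47 standard errors, and neither would be conclusive.

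Third, tables of related TEAEs are planned, all eCRF data will be listed, Section 8.3.5 allows further exploratory analysis, and a separate SAP, not among the documents, may add period tables. These soften the point. Still, relatedness rests on the investigator's judgement, and listings give no rates by arm.

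A reader might infer more than the documents support:
- That any drug effect is diluted. Terms rare off drug, such as injection-site or infusion reactions, are hardly affected.
- That pooling is why the routes cannot be separated. The cause is the design, IV then SC in every subject. Effects local to the SC site are covered by a primary endpoint of their own.
- That no planned summary uses the IV-only hours. Vital-sign and Day 1 laboratory summaries do.
- That the worst-grade rule drops subjects. It changes only which grade is shown: a later, worse event of the same term can mask the grade seen on treatment.

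**Conclusion.** The point holds as a gap in Section 8.3.2.1. The TEAE window has no end, 75.6% of it follows the last scheduled dose, and no listed AE table separates onset during treatment from onset in follow-up. For terms with appreciable background in recovery, this makes an on-treatment excess harder to see. In the main illustration the ratio falls from 1.94 to 1.24 and the difference from about 5.6 to 4.8 points. Every rate behind these figures is assumed, and the size depends on the background risk after treatment and on how early background events fall.

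That systemic effects of the two routes cannot be separated is a separate limit set by the design. No table can remove it, because all events after the first SC dose follow both routes. This is a worthwhile and inexpensive improvement. It does not show that the 90-day analysis is wrong, or that the separate SAP lacks such tables.

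**What to change.** In Section 8.3.2.1, keep the 90-day TEAE tables. Beside them, add the overall summary, SOC/PT, maximum-severity and SAE tables by onset period, counting each subject once within each period:

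- (a) start of infusion to just before the first SC dose;
- (b) first SC dose to the last dose received plus a pre-specified residual window, for example one 72-hour dosing interval;
- (c) from then to Day 90.

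Show (a) and (b) combined as an on-treatment table, next to the 90-day table and not in place of it. Fix the end of (b) before unblinding. State that (a) describes early infusion tolerability only, and that later events follow both routes.

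The cost is protocol or SAP wording and a few more tables. AE onset date and time are already collected, and visits and sample size do not change. The drawbacks are small counts in (a) and an end to (b) that is a convention.

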#### *8.3.2.2 Physical Examination Findings*

Physical examination data for all time points assessed will be summarized, including Investigator assessment of clinical significance for abnormal findings. Shift tables from baseline to days 4, 22, 56 and 90 may also be generated, as applicable.

#### *8.3.2.3 Vital Signs*

All vital sign parameters will be summarized using descriptive statistics for each treatment group for all time points assessed, including change from baseline for all post-dose assessments. Shift tables from baseline to post-dose assessments may also be generated, as applicable.

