In repeated dosing studies, administration of DM199 by SC injection at dose levels of 1.44, 2.88 and 3.6 mg/kg/day for 28 days was well tolerated in rats. There were no DM199 associated findings for clinical observations, body weights, food consumption, ophthalmic observations, hematology, clinical chemistry, coagulation, urinalysis, gross pathology observations, or organ weights and ratios. Administration of DM199 by SC injection for 1 month was well tolerated in cynomolgus monkeys at all dose levels. A single high dose female animal was euthanized for humane reasons on Day 8 for telemetry implant-related complications that were not due to test article administration. DM199-related findings were limited to a non-dose-related microscopic finding at the injection site at all dose levels and an increase in liver-specific enzyme serum levels at 1.44 mg/kg/day. Based on these results, the no observable adverse effect level (NOAEL) was considered to be 1.44 mg/kg/day.

Treatment with DM199 in rodent models of type 2 diabetes mellitus restored insulin sensitivity and improved insulin secretion. Treatment of non-obese diabetic mice attenuated the development of autoimmune reaction that results in type 1 diabetes mellitus. At 7 weeks of treatment, the non-obese diabetic mice developed a 6-fold increase in circulating C-peptide without a detectable increase in insulin, episodes of hypoglycemia or increase in beta cell mass.

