### **7.4.1 Source Documentation Reporting Requirements**

Images and corresponding reports for any brain imaging completed as part of standard of care treatment for any enrolled subject throughout the duration of the study (i.e. initial presentation through withdrawal) will be submitted to the CRO. In addition, it may be necessary from time to time to submit other source documents to the CRO or Sponsor to allow for timely safety discussions (i.e. expedited reporting of SAEs).

All source documents submitted to the Sponsor or its representatives, including imaging and reports, must be de-identified according to local and federal confidentiality requirements and identified by the subject number.

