#### **8.1.2 Sample Size**

No formal sample size estimation was performed. Up to 66 subjects will be enrolled to achieve approximately 60 completed subjects, based on an estimated drop-out rate of 10%. Subjects will be randomized 1:1 to receive DM199 or placebo, resulting in 33 enrolled subjects per treatment group. A sample size of 30 completed subjects in each treatment group is considered adequate to evaluate the safety and tolerability of DM199. Should a subject drop out, the drop out subject may be replaced by a subject assigned to the same treatment arm as the drop out subject.

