#### *8.3.2.4 Hematology and Chemistry*

All hematology and chemistry (continuous variables) parameters will be summarized using descriptive statistics for each treatment group for all time points assessed, including change from baseline for all post-dose assessments. Shift tables from baseline to days 4, 22, 56 and 90 will also be generated for each safety laboratory parameter with values of Within Normal Limits (WNL), High, and Low used for the shift categories.

Laboratory values will be compared to normal range of the laboratory and values that fall outside of the normal ranges will be flagged as: H (High) and L (Low) in the data listings.

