## **9 RISK/BENEFIT ANALYSIS**

### **9.1 POTENTIAL RISKS**

Previous pre-clinical and clinical studies have shown DM199 to be generally safe and well-tolerated, with postural hypotension as a drug-related side effect demonstrated at high doses (refer to **1.2 Nonclinical Summary** and **1.3 Clinical Summary**). The effects of the study treatment on human pregnancy and the unborn fetus are unknown.

Refer to the Investigator's Brochure for full investigational product information including a comprehensive listing of known safety information.

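### No planned safety table counts or grades, per arm, the subjects with marked blood-pressure falls or laboratory abnormalities, so an effect in a few subjects would be hard to compare between arms

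*Combined protocol and SAP*

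**What the plan says.** Vital signs, hematology, chemistry, ECG and physical examination changes are components of the primary safety endpoint beside adverse events (section 8.2.1). Section 8.3 rules out formal comparison of the arms, so the descriptive tables are the whole primary analysis.

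- **Vital signs (8.3.2.3).** "All vital sign parameters will be summarized using descriptive statistics for each treatment group for all time points assessed", with change from baseline. Section 8.3 defines descriptive statistics for continuous variables as N, mean, SD, median, minimum and maximum. Shift tables are optional, and no categories are given for them.
- **Laboratory (8.3.2.4).** The same statistics and change from baseline, plus mandatory shift tables "for each safety laboratory parameter with values of Within Normal Limits (WNL), High, and Low used for the shift categories". Listings flag values as high or low.
- **Adverse events (8.3.2.1).** Tables by SOC and PT, by maximum severity and by maximum relationship, with separate tables for serious and for Grade 3 or higher events, overall subject counts, and by-subject listings. A subject is counted once within a SOC or a PT.
- **Grading.** Section 6.4.1 adopts CTCAE v4.03 for adverse events. Section 8.3.2.4 does not apply it to laboratory values.
- **Named risks.** Section 9.1 describes DM199 as generally safe, "with postural hypotension as a drug-related side effect demonstrated at high doses". Section 4.5 singles out hypotension, hypoglycaemia and infusion-related reactions.
- **Deferral.** Section 8.3 leaves detailed methods to a separate SAP due before database lock. That document is not among those supplied.

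**The concern.** A drug effect confined to a few subjects is best displayed as a count of affected subjects in each arm. For blood pressure the planned output is organised by visit, so a reader sees how extreme the worst reading was at each visit but cannot add up subjects across visits. For laboratory values the only categorical output has three levels and discards the degree of abnormality. For adverse events, related terms for one clinical problem may fall in different PT rows.

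At stake is whether the primary safety tables allow a like-for-like comparison on the risk that the protocol itself names. Otherwise the reader must go to the listings and choose cut-offs once the data are known.

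**Working it through.** **1. The plan's own figure.** "No formal sample size estimation was performed", and "Subjects will be randomized 1:1 to receive DM199 or placebo, resulting in 33 enrolled subjects per treatment group" (section 8.1.2). Checking 60 completers at 10% drop-out: 60 × 1.10 = 66, or 30 × 1.10 = 33 per arm. The alternative formula gives 60 / 0.90 = 66.7, rounded up to 67. The stated figures reproduce to within one subject. No power, event rate or blood-pressure SD is given, so every blood-pressure input below is an assumption, shown as a range.

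**2. What the mean can show.** Suppose k of 33 DM199 subjects have an extra 40 mmHg systolic fall at one visit.

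- Shift in the arm mean = 40k / 33: 1.2, 2.4 and 3.6 mmHg for k = 1, 2 and 3.
- SE of the difference between arms = SD × √(2/33): 2.5, 3.7 and 4.9 mmHg for a change SD of 10, 15 and 20.

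In a simulation of 20,000 trials per setting, a nominal 95% interval for the difference lay wholly below zero in about 4% to 14% of trials. The plan makes no such test; this only shows that the mean carries little information here.

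**3. What the minimum can show.** Same simulation, chance that the DM199 minimum is the lower of the two (50% with no effect):

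| Change SD | k = 1 | k = 2 | k = 3 |
|---|---|---|---|
| 10 | 97% | 99.5% | 99.9% |
| 15 | 81% | 91% | 95% |
| 20 | 69% | 79% | 85% |

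So the planned minimum usually reacts. If three subjects fall at three different visits, each visit is in the k = 1 column. A row of visit minima also cannot tell three subjects falling once each from one subject falling three times.

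**4. The laboratory shift rule.** Take ALT as a multiple of the upper limit.

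- 1.1 to 6.0: high at both times, so no shift.
- 0.95 to 1.05: normal to high, so a shift.

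The rule ignores a rise of 4.9 times the limit and counts one of 0.10. The planned maximum would show the value of 6, but not how many subjects reached such levels in each arm.

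**5. Term splitting.** If three DM199 subjects have hypotension-related events coded to three different PTs, the PT table shows three rows of 1/33 (3.0% each). A pooled row shows 3/33 (9.1%).

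**6. What a worst-value count would show with no drug effect.** Section 5.6 gives nine post-dose readings through Day 22: two on Day 1, and one each on Days 4, 7, 10, 13, 16, 19 and 22. For independent normal changes, the expected number of 33 subjects with at least one fall of 40 mmHg or more is 33 × [1 − (1 − Φ(−40/SD))⁹].

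- SD 10: 33 × 0.0003 = 0.01.
- SD 15: 33 × 0.034 = 1.1.
- SD 20: 33 × 0.187 = 6.2.

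By simulation with a correlation of 0.8 between readings, these become about 0.01, 0.5 and 2.5. The count therefore has a background that depends on the SD, and has meaning only beside the placebo count.

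**The case against.** The strongest reply is that the plan already displays extremes. Minimum and maximum are required at every visit, including for change from baseline. Laboratory parameters have full continuous summaries beside the shifts. Serious and Grade 3 or higher events have their own tables, and the overall counts of subjects with such events do not depend on how terms are split. Clinically significant vital-sign and laboratory abnormalities become adverse events (sections 5.9.1 and 6.2.4), an independent DSMB reviews safety, and all eCRF and central laboratory data are listed. All of this stands. A reader might infer that blood pressure is reported only as means, that adverse events are reported only by preferred term, or that a severe effect in a few subjects would not show. The documents contradict each of these.

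Two parts of the reply do not close the gap. Conversion to an adverse event rests on site judgement with no common threshold, and vital signs and laboratory values are primary components in their own right. Listings are not a between-arm summary.

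It is also fair that the separate SAP may supply these tables, and that vital signs are taken seated after five minutes' rest, so a worst seated fall does not isolate the postural hypotension described in section 9.1. Both limits are accepted.

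The liver-enzyme illustration should not be over-read. The monkey study reported "an increase in liver-specific enzyme serum levels at 1.44 mg/kg/day", but section 1.2 treats that dose as the no-adverse-effect level. Per kg it is 1,440 / 3 = 480 times this trial's single SC dose.

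**Conclusion.** The point holds as a gap in counting and grading. As written, no planned table gives, per arm, the number of subjects with a marked blood-pressure fall, the grade reached by a laboratory abnormality, or the number with any hypotension-related event. The laboratory rule is the clearest defect, because it follows from the stated text and needs no assumption. The blood-pressure part rests on an assumed 40 mmHg fall, normal data and a change SD of 10 to 20: the mean moves 1.2 to 3.6 mmHg against an SE of 2.5 to 4.9, and the minimum usually moves but does not count subjects.

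Three stronger readings are not supported:

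- That harm in a few subjects is the likeliest form at this sample size. No figure in the documents supports it.
- That a worst-value table would give a clean contrast of affected DM199 subjects against none on placebo. At an SD of 20, about 2.5 to 6 of 33 unaffected subjects would reach a 40 mmHg fall by ordinary variation.
- That the brain images sent to the CRO under section 7.4.1 form part of this gap. They are standard-of-care images, not taken systematically, and raise a separate question.

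The additions are worth making before the SAP is final. They affect neither the conduct of the trial nor its sample size.

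**What to change.** In the SAP, and in section 8.3 if the protocol is amended:

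1. **Section 8.3.2.4.** For analytes that CTCAE v4.03 grades, replace the normal/high/low shift table with the shift from baseline grade to worst post-baseline grade, by arm. Keep high/low flags for listings and for analytes without a grade.
2. **Section 8.3.2.3.** Summarise each subject's largest post-dose fall from baseline in systolic and in diastolic pressure over Days 1 to 22. Give the number and percentage per arm at or beyond cut-offs fixed before unblinding, always with placebo alongside. The cut-offs are analysis categories only and carry no implication for treatment. State the number of subjects with at least one post-dose reading.
3. **Section 8.3.2.1.** Add one pooled row per arm for hypotension-related terms, and one for each of the other events named in section 4.5, with the term lists fixed before unblinding.

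**Cost.** A few extra tables and the term lists. No new assessments are needed. The limits to state beside the tables are that the worst of nine readings picks up ordinary variability (about 0, 0.5 to 1, or 2.5 to 6 of 33 unaffected subjects at 40 mmHg for a change SD of 10, 15 or 20), and that seated readings do not isolate postural drops.
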